5.1.3.5 Other Commercially Available Agents in the Vaccines

Montanide ISA-51 will be purchased from SEPPIC Inc. (www.seppic.com) and stored at UPMC IMCPL. Each enrolling site will receive Montanide from UPMC IMCPL once a patient is enrolled. Please refer to the PNOC secure SharePoint Member Website for details on how to request Montanide as well as for the SOP on how to prepare the final peptide emulsion that will be administered to the patient.

5.1.3.6 Toxicities (K27M/TT Vaccine)

Chronic inflammatory reactions are expected to occur in all patients at their vaccine sites. Induration may persist for months, but is not expected to require additional therapy. Sterile abscesses may occur

in some patients. These are not a basis for discontinuation of the vaccines. However, if the inflammatory reactions are severe, subsequent vaccines may be administered in adjacent skin (< 2 cm from prior injection site) rather than in the same location(s), to minimize additional morbidity. In the event the vaccine cannot be administered within 2 cm of the designated site(s), vaccination site(s) will be assigned on the corresponding location of the contralateral side. Poly-ICLC will be administered intramuscularly on the same side as the vaccine on the same day the vaccine is administered. Complete and updated adverse event information is available in the Investigator's Brochure.

5.1.4 Poly-ICLC

Poly-ICLC is classified as an investigational drug. It is a synthetic complex of polyinosinic and polycytidylic acid, stabilized with polylysine and carboxymethyl cellulose. The thermal denaturation point is 89.5°C, about 40°C above that of plain Poly-ICLC; the resistance to hydrolysis is several times that of the parent compound, and it induces peak levels of about 1000-2000 IU of interferon-□□per mL of serum in monkeys given 1 mg/kg intravenously.

5.1.4.2 Availability (Poly-ICLC)

Poly-ICLC is prepared and packaged in the GMP facility of Bioserv, Corp. It is then tested for activity and pyrogenicity by Oncovir, Inc. Each site will request poly-ICLC from UPMC-IMCPL through the PNOC Operations office after a patient has been enrolled into the trial. To order poly-ICLC please refer to the secure PNOC SharePoint member website.

5.1.4.3 Storage & Stability (Poly-ICLC)

Poly-ICLC is supplied in vials containing 1mL of translucent solution with a concentration of 1.8 mg/mL. It is stable at room temperature for several days, but is better stored refrigerated at about 40°F (not frozen).

5.1.4.4 Toxicities of Poly-ICLC

Flu-like symptoms:

The main toxicity of poly-ICLC is a flu-like reaction including fever, myalgias, arthralgias, malaise, and possibly nausea and vomiting. The severity is dependent on dose, route of injection and overall health of the participant. Early Phase I studies were done to determine the maximum tolerated dose (MTD) under the assumption that this was also the most effective dose. In these studies of cancer patients, it was found that the MTD was about 12 mg/m² IV in patients who were not terminally ill. Patients typically showed fevers of 40°C, myalgias, arthralgias, malaise, and nausea and vomiting. Fever was the primary dose-limiting factor. At this dose, the mean serum IFN level was 2000 IU/mL. While giving exogenous IFN rarely attains this level, levels of 100 IU/mL in response to exogenous IFN are associated with the same types and degree of adverse effects as seen with high dose poly-ICLC. In most of the early cancer trials, about 6 mg/m² poly-ICLC IV was generally used.

It was subsequently shown that low doses (i.e., low dose poly-ICLC) were superior to higher ones for enhancing immune effects, and that the higher dose actually inhibited a number of cell-associated immune functions. It was also found that intramuscular injection produced milder side effects than IV

administration ³³. The most common symptom has been mild, transient discomfort at the injection site. On occasion, 8 to 12 hours after doses of 10 to 50 micrograms/kg IM, patients may also develop a mild flu-like syndrome with fever of less than 38°C, which may last for another 12 hours, but responds readily to acetaminophen or aspirin. Mild myalgias, arthralgias, sometimes nausea, and malaise are present during this period of time. This flu-like syndrome typically diminishes markedly after the first few poly-ICLC treatments.

Hematologic:

Poly-ICLC has been associated with a coagulopathy in dogs, but not in other species (including primates); and there has been no change in the expected incidence of deep venous thrombosis, pulmonary embolus, or coagulopathy in multiple sclerosis, AIDS or malignant glioma patients on low dose IM poly-ICLC. One paralyzed multiple sclerosis participant treated with 100 micrograms/kg suffered a fatal pulmonary embolus which was not confirmed to be related to the drug-administration. Transient leucopenia, lymphopenia, or granulocytopenia has been reported in malignant glioma patients on poly-ICLC. In the completed North American Brain Tumor Consortium trials (n=76 patients), in which patients received IM poly-ICLC three times/week (20 micrograms/kg), of 786 events reported, there were 23 grade 1 or 2 granulocytopenias, 32 grade 1 or 2 leukopenias, and 17 grade 1 or 2 lymphopenias. Three patients had grade 3 leukopenia. Animal studies demonstrated that a major portion of IFN-induced leucopenia is related to transient sequestering of WBC in lymphoid organs.³⁰

Hepatic enzyme elevation:

Mild (grade 1), transient (<7 days) hepatic enzyme elevations were described in a trial of 100 micrograms/kg poly-ICLC given intravenously in multiple sclerosis patients. In three patients this was prolonged >7 days, but in all patients the enzymes returned to normal after temporary discontinuation of the poly-ICLC.

Seizures:

Three glioma patients with epilepsy had seizures during the febrile episode after poly-ICLC, but recovered uneventfully. Whether this reaction represented inadvertent IV injection on those occasions is uncertain.

Pseudo-Tumor Progression:

In the malignant glioma pilot trial in adults²⁷ a few patients showed increased contrast enhancement with or without increased edema 2-4 months after the initiation of poly-ICLC administration, followed by an apparent tumor response at 6-12 months. Dexamethasone was used if clinically indicated during the time of pseudo-tumor progression. In a more recent NABTC study, in adult patients with advanced recurrent gliomas, several patients have shown a similar phenomenon after several weeks of poly-ICLC therapy, which resolved with or without concomitant steroids (patients continued their poly-ICLC administration during this time). Biopsy of a tumor demonstrating increased contrast enhancement in

one patient receiving dendritic cell-based vaccines showed inflammation rather than recurrent tumor²⁷. These findings raise the possibility that vaccines and poly-ICLC may at times be facilitating a relatively early immunologic anti-tumor response, manifested by increased edema and/or contrast enhancement on MRI. Once treatment is started, patients will be closely monitored with serial MRI scans and neurologic evaluations to assess for treatment response as well as pseudo-tumor progression.

To minimize the likelihood that the timing of radiotherapy-induced swelling or increased enhancement may coincide with the pseudo-tumor progression caused by poly-ICLC, we will defer the initiation of poly-ICLC/vaccine for up to 12 weeks post-RT in strata A, B and C in those patients that experience clinically symptomatic radiographic worsening (i.e. increased enhancement/mass effect on MRI scan) immediately following irradiation, to allow this response to resolve.

Experience in pediatric patients with glioma:

As reviewed in Section 1.2, a multi-institutional trial of poly-ICLC in pediatric patients with brain tumors enrolled a total 46 patients. An improved and prolonged response was seen in one patient in whom the poly-ICLC dose was increased from 20 micrograms/kg to 30 micrograms/kg given twice a week IM, so that a dose of 30 micrograms/kg was used in subsequent patients and well tolerated. There were 16 incidents of Grade 3 or 4 reported adverse events but most of them were unlikely to be related to the therapy. There were 4 cases of Grade 3 hepatic toxicity and one case of Grade 3 fever, which were considered to be possibly or definitely related to the therapy, respectively. A case with Grade 3 and another case with Grade 4 neurological toxicity were noted but both cases manifested clinical and radiological signs of tumor progression (personal communication Oncovir).

In the pediatric trial using GAA specific peptides, poly-ICLC (Hiltonol, Oncovir, Washington DC) was also used at a dose of 30micrograms/kg and this dose was well tolerated. Based on these observations, we will also use poly ICLC at 30micrograms/kg in the current protocol¹⁴.

5.1.5 Summary of Common AEs

The most common AEs from the combination of K27M/TT, Montanide and poly-ICLC (≥ 25% of patients) include injection site reaction, white blood cell decreased, vomiting, fatigue, alanine aminotransferase increased, aspartate aminotransferase increased, lymphocyte decreased, headache and skin induration.

Update: As of 12/31/18, treatment with the K27M/TT vaccine and poly-ICLC has been proven to be well tolerated with one RLT in the total 29patients treated on strata A and B, 19 and 10 patients in each stratum, respectively.

5.1.6 Nivolumab

Structure and molecular weight

Nivolumab is a monoclonal antibody consisting of 4 polypeptide chains, which include 2 identical heavy chains consisting of 440 amino acids and 2 identical light chains. Molecular weight is 146,221 Daltons.

Supplier

Nivolumab will be supplied by Bristol-Myers Squibb (BMS). Do NOT use commercially available supply.

Formulation

The agent is a clear to opalescent, colorless to pale yellow liquid, with light (few) particulates. It is available in a 100 mg/10 mL vial containing a sterile, non- pyrogenic, single-use, isotonic aqueous solution formulated at 10 mg/mL in sodium citrate, sodium chloride, mannitol, diethylenetriamine pentaacetic acid (pentetic acid) and polysorbate 80 (Tween® 80) to a pH of 6.0. A small amount of overfill (0.7 mL) is included with each vial to account for VNS (vial, needle, syringe) loss. The 10 mL type I flint glass vials are stoppered with butyl rubber stoppers and sealed with aluminum seals.

Storage

Nivolumab vials for injection must be stored at 2° – 8° C (36° – 46° F) and protected from light, freezing and shaking.

Solution Preparation

Nivolumab injection can be infused undiluted (10 mg/mL) or diluted with 0.9% Sodium Chloride Injection, USP or 5% Dextrose, USP to a final concentration of 1 - 10 mg/mL. Vial contents from different lots should not be mixed in the same infusion.

Stability

The administration of undiluted and diluted nivolumab must be completed within 24 hours of preparation. If not used immediately, the infusion solution of nivolumab injection prepared for dosing may be stored for up to 24 hours in a refrigerator at 2°-8°C (36°-46°F) and a maximum of 8 hours of the total 24 hours can be at room temperature (20°-25°C, 68°-77°F) and under room light. The maximum 8-hour period under room temperature and room light conditions for nivolumab injection in IV bag includes the product administration period (30 minutes). Vials of nivolumab for injection do not contain preservatives or bacteriostatic agents and should be prepared as soon as possible prior to administration using aseptic technique.
5.2 Drug Accountability

Each PNOC site Investigational Pharmacist will manage drug accountability records per site standards.

5.3 Drug Ordering

The K27M/TT peptide vaccine will be ordered from UPMC -IMCPL through the PNOC Operations office. Please refer to the PNOC SharePoint Member Website for detailed order instructions and an order request form.

The poly-ICLC will be ordered by each PNOC site directly through PNOC Operation's Office and shipped from UPMC -IMCPL- please refer to the PNOC SharePoint Member Website for detailed order instructions and an order request form.

Each investigational pharmacy will order Montanide (Seppic, Inc.) from UPMC -IMCPL through the PNOC Operation's Office to generate the K27M/TT peptide-based vaccine per SOP just prior to administration of the vaccine. Please refer to the PNOC SharePoint Member Website for detailed order instructions and an order request form.

Nivolumab: Nivolumab will be ordered via manual drug order form. Drug supply will be shipped by BMS vendor Fisher Scientific. More detailed instructions are available via the PNOC SharePoint Member Website.

6 Treatment Plan

Eligible patients will undergo focal radiation therapy after initial diagnosis as part of their standard of care per institutional guidelines. **Stratum A** patients **must** begin radiation therapy within 4 weeks of diagnosis by imaging or pathology, whichever is later. **Stratum B** patients **must** begin radiation therapy within 4-6 weeks from surgery (for those subjects undergoing surgery for more extensive resection). **Stratum C:** Patients with DIPG **must** begin radiation therapy within 4 weeks of diagnosis by imaging or pathology, whichever is later. Patients with other midline gliomas, excluding primary spinal cord tumors, **must** begin radiation therapy within 4-6 weeks from surgery for more extensive resection).

Treatment should start 2-8 weeks after completion of radiation therapy for all strata. Children will receive subcutaneous injections of synthetic peptides of the H3.3.K27M epitope and tetanus toxoidderived helper epitope (K27M/TT) emulsified in Montanide ISA-51 along with concurrent intramuscular injections of immunoadjuvant poly-ICLC every **3 weeks for a total of 8 doses** (please see **Therapy Schema** for trial design). Stratum C patients will also receive nivolumab.

Strata A & B: If the subject demonstrates stable to improved disease to the vaccine therapy and tolerates the therapy well (defined as not having any regimen related toxicities RLT; see below), patients may receive additional vaccinations every 6 weeks after the 8th dose starting at Week 30 for a total of 96 weeks (approximately 2 years).

Stratum C: On the same day (+/- 3 days) as the vaccination with K27M/TT and poly-ICLC, stratum C patients will receive nivolumab 4.5 mg/kg IV, every 3 weeks, through week 21 of the study procedures. If the subject demonstrates stable to improved disease to the vaccine therapy and nivolumab combination therapy and tolerates the therapy well (defined as not having any regimen related toxicities RLT; see below), stratum C patients may continue to receive nivolumab every 3 weeks after the 8th dose for a total of 96 weeks (approximately 2 years). Patients may receive additional vaccination with K27M/TT and poly-ICLC combined with nivolumab every 6 weeks after the 8th dose and will resume combination therapy, starting at Week 27, for a total of 96 weeks (approximately 2 years).

Because the peptide vaccine is sequestered locally and the immune response occurs primarily locally, the dose of the vaccine does not need to be scaled up proportionately to weight or body surface area; however, nivolumab will be based on the weight measured within 7 days prior to each infusion. With regard to the dose of poly-ICLC we will use a fixed amount of 30 micrograms/kg, which was used previously and demonstrated good tolerability with only grade 1-2 adverse events (injection site reactions, flu like and GI symptoms)¹⁴. The K27M/TT specific peptide will be emulsified in the adjuvant Montanide ISA-51, which consists of a mineral oil base, which has demonstrated to be well tolerated in previous studies¹⁴.

- 6.1 Dosage and Administration
- 6.1.1 Dosage
- 6.1.1.2 Poly-ICLC

Justification for the proposed dose of poly-ICLC (30 micrograms/kg IM) is provided in Section 1.2 and Section 5.1.4.4 (Experience in pediatric patients with glioma). The first course of poly-ICLC administration (30 micrograms/kg IM) will be administered on the day of the first K27M/TT vaccine, unless the patient has evidence of radiation induced pseudoprogression as outlined in Section 5.1.4.4 (Pseudo-tumor progression). If that is the case, administration of poly-ICLC can be deferred for up to 12 weeks. For each of the following repeated vaccinations, poly-ICLC (30 micrograms/kg IM) will be administered on a recent pilot study of peptide-based vaccines in DIPG patients, in which the combination of peptide-vaccine and IM administration of poly-ICLC (30 micrograms/kg) administered on the same day induced robust antigen-specific T-cell responses.¹⁴

Dose should be verified with each administration as per standard chemotherapy procedures. Dose adjustments should be done if there is a \geq 10% weight change from the prior dose.

Pretreatment with acetaminophen or with any NSAID should be given before each poly-ICLC dose.

Reported adverse events and potential risks are detailed in Section 5.1.4.4. Appropriate dose modifications for poly-ICLC are described in Section 6.2.1.

6.1.1.3 K27M/TT Peptide Vaccine

Because the peptide vaccine is sequestered locally, and the immune response occurs primarily locally and in the draining lymph nodes, the dose of the vaccine does not need to be scaled up proportionately to the size (by weight or body surface area) of the recipient, as might be done for a drug whose effect is related to its distribution in body fluid. Because direct toxicity of the peptide is not expected, dose escalation is not as meaningful as it would be with a drug with a narrow therapeutic index. The proposed dose is based on past trials, in which up to 1 mg for each of tumor-antigen peptide emulsified in Montanide ISA-51 were safely administered. The 1 ml K27M/TT solution ordered by each site contains 750 micrograms/ml K27M peptide and 500 micrograms/ml TT peptide. Eight hundred (800) microliters (μ L) of that aqueous solution, which corresponds to 600 micrograms K27M peptide and 400 micrograms TT will be mixed 1:1 with Montanide ISA-51 to form one water-in-oil emulsion. The injection volume is 800 microliters (μ L), which contains a final peptide amount of 300 micrograms and 200 micrograms of the TT. Ideally, the vaccine should be administered within 2 hours after mixing, however it is stable up to 6 hours at room temperature. If the vaccine is not administered within 6 hours after mixing, it should be discarded.

6.1.1.4 Nivolumab

Nivolumab will be given intravenously every 3 weeks at 4.5 mg/kg per dose over 30 minutes. Premedication is not required as infusion reactions are rare, but anaphylactic precautions should be observed during each infusion with nivolumab. If grade \geq 2 infusion reaction occurs, the infusion should be stopped and supportive care given based on institutional guidelines. Please refer to Section 6.2.3 for dose modifications for nivolumab. The drug dose should be adjusted based on the patient's actual weight in kilograms measured within 7 days prior to the beginning of each infusion.

6.1.2 Treatment Administration

Treatment will be administered on an outpatient basis. Patients will be vaccinated subcutaneously in the upper arm or thigh. Since we mix the K27M peptide and the TT-helper peptide in one emulsion (0.8 mL), there will be one injection for the peptide vaccination and one intramuscular (IM) injection for poly-ICLC. Poly-ICLC is expected to enhance the antigen-presentation process in the draining lymph nodes, and therefore poly-ICLC should be administered intramuscularly (IM) within close vicinity to the peptide-injection site (less than 3 cm from the center of the peptide injection sites).

In each vaccination, the location of vaccination will remain at the same site. Numbing measures such as creams, ice or mechanical devices are not permitted. Per Section 5.1.3.6, if the skin reaction from the previous vaccine does not allow the next administration at the same site, the vaccine may be administered in adjacent skin (< 2 cm from the prior injection site). If the vaccine cannot be administered within 2 cm of the designated site, the vaccine site will be administered on the contralateral side. Poly ICLC will be administered intramuscularly on the same side and on the same day as the K27M/TT vaccine was administered.

The K27M/TT vaccine will be administered every three weeks starting 2-8 weeks following the completion of radiation therapy. Vaccine will be administered every 3 weeks up to and including Week

21 (8 doses). For strata A and B, vaccination will resume on Week 30 and every 6 weeks thereafter. For stratum C, vaccination will resume on Week 27 and every 6 weeks thereafter.

Poly-ICLC is administered IM using sterile technique, as supplied from the vial and in the amount prescribed for the participant's weight (typically, one vial is sufficient for one dose). The poly-ICLC treatments will be administered on the same day as the vaccine, sequentially after K27M/TT administration. Vital signs will be monitored before and for at least 20 minutes after each treatment.

Nivolumab should be given intravenously on the same day as the vaccine or within 3 days (+/- 3 days) of vaccination. It can be given before or after the vaccination but should ideally be given on the same day as vaccination with K27M/TT and poly-ICLC.

Nivolumab Injection, 100 mg/10 mL (10 mg/mL) and 40 mg/4 mL (10 mg/mL) nivolumab injection is to be administered as an IV infusion through a 0.2-micron to 1.2-micron pore size, low-protein binding in-line filter at the protocol-specified doses. It is not to be administered as an IV push or bolus injection; any programmable infusion pump may be used. Nivolumab injection can be infused undiluted (10 mg/mL) or diluted with 0.9% Sodium Chloride Injection, USP or 5% Dextrose Injection, USP to protein concentrations as low as 0.35 mg/mL. Dilution and infusion of nivolumab should be carried out per institutional standard and as per section 5.1.5. Care must be taken to assure sterility of the prepared solution as the product does not contain any antimicrobial preservative or bacteriostatic agent. Nivolumab infusions are compatible with polyvinyl chloride (PVC) or polyolefin containers and infusion sets, and glass bottles.

6.2 Dose Modifications and Dosing Delays

The following dose modification rules will be used with respect to potential toxicity. Toxicity will be assessed according to the NCI Common Terminology Criteria for Adverse Events Version 5.0 (CTCAE v5.0).

6.2.1 Dose Modifications for Poly-ICLC

For grade 2 or greater constitutional symptoms (see Section 5.1.4.4) that are considered related to treatment that persist for greater than 48 hours after the injection, the next poly-ICLC dose should be given at two-thirds of the original dose (20 micrograms/kg). If further dosing is well tolerated, the original dose may be subsequently re-instituted at the discretion of the investigator. All dosage changes will be recorded in Advarra. If grade 2 or greater symptoms again occur despite one dose reduction and last > 48 hours, the patient will not receive any more poly-ICLC but can continue to receive the K27M/TT peptide if patient is stable.

In the case of treatment-related hepatic enzyme elevation > 5x baseline (grade 3 or greater), or any related, intolerable grade 2 or greater non-hematologic toxicity that lasts for \geq 7 days, poly-ICLC will be held until that toxicity has reduced to Grade 1 or less. Poly-ICLC will then be re-administered at two-thirds of the original dose (20 micrograms/kg), and the participant will be closely observed. If the same dose-limiting toxicity again recurs despite the dose reduction, the participant will continue to receive the K27M/TT peptide without poly-ICLC if patient is stable.

For treatment-related grade 3 or greater hematologic toxicity, the next dose should be reduced to two thirds of the original dose (20 micrograms/kg) as long as the toxicity has resolved to grade 1 or less by the time the next dose is due. If the toxicity has not resolved by the time the next dose is due, the patient is off treatment with poly-ICLC but can continue with the K27M/TT peptide vaccination per schedule.

See Section 6.2.4 below for pseudo-tumor progression guidelines (presumed or proven) that require a temporary discontinuation of treatment.

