- The patient must have adequate organ function defined as:

Adequate Bone Marrow Function Defined as:

- Peripheral absolute neutrophil count (ANC) ≥ 1000/mm³ and
- Platelet count ≥ 100,000/mm³ (transfusion independent, defined as not receiving platelet transfusions for at least 7 days prior to enrollment).

Adequate Renal Function Defined as:

- Creatinine clearance or radioisotope GFR ≥ 70mL/min/1.73 m² or
- A serum creatinine based on age/gender as follows:

Age	Maximum Serum Creatinine	
	Male	Female
3 to < 6 years	0.8	0.8
6 to < 10 years	1	1
10 to < 13 years	1.2	1.2
13 to < 16 years	1.5	1.4
≥ 16 years	1.7	1.4

The threshold creatinine values in this table were derived from the Schwartz formula for estimating GFR utilizing child length and stature data published by the CDC.

Adequate Liver Function Defined as:

- Bilirubin (sum of conjugated + unconjugated) ≤ 1.5 x upper limit of normal (ULN) for age **and**
- SGPT (ALT) ≤ 110 U/L and
- Serum albumin \geq 2 g/dL.

Adequate Pancreatic Function Defined as:

• Serum lipase \leq ULN at baseline.

Adequate Pulmonary Function Defined as:

• No evidence of dyspnea at rest, no exercise intolerance due to pulmonary insufficiency, and a pulse oximetry of > 92% while breathing room air.

Adequate Neurologic Function Defined as:

- Patients with seizure disorder may be enrolled if seizure disorder is well controlled.
- The effects of the H3.3K27M vaccine and nivolumab on the developing human fetus are unknown. For this reason, females of child-bearing potential and males must agree to use adequate contraception. Adequate methods include: hormonal or barrier method of birth control; or abstinence prior to study entry and for the duration of study participation. Should a woman become pregnant or suspect she is pregnant while she or her partner is participating in this study, she should inform her treating physician immediately. Males treated or enrolled on this protocol must also agree to use adequate contraception prior to the study and for the duration of study participation.
- Ability to understand a written informed consent document, and the willingness to sign it. Assent will be obtained when appropriate based on the subjects age.

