6.3 Regimen Limiting Toxicity (RLT)

Each patient receiving K27M/TT peptide vaccination and poly-ICLC or K27M/TT peptide vaccination and poly-ICLC in combination with nivolumab will be evaluable for safety. The safety parameters include all laboratory tests and hematological abnormalities, physical findings, and spontaneous reports of adverse events reported to the investigator by patients.

RLT includes any of the following events that occur during the first 8 vaccine doses (the entirety of the time from the 1st vaccine administration through the 8th vaccine administration) and up to 30 days after the 8th vaccine administration and are considered either possibly, probably, or definitely to the vaccine:

- Any grade 2 or greater autoimmune reaction.
- Any grade 3 or greater hematologic or non-hematologic toxicity with the exception of lymphopenia.
- Any life-threatening event.
- Any other unexpected Grade 2 or greater neurological deficit, which is possibly, probably, or definitely related to the vaccine therapy that does not respond within 21 days trial of 0.3mg/kg day dexamethasone or equivalent (max 12mg/day) or Avastin equivalent (10mg/kg every 2 weeks for a maximum of 3 doses)

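### Section 6.2.1 equates a fivefold rise over baseline in hepatic enzymes with grade 3, so the poly-ICLC hold rests on two scales and nothing says which governs

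*Combined protocol and SAP*

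**What the plan says.** All references are to the combined protocol and SAP.

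- **Trigger (6.2.1).** "In the case of treatment-related hepatic enzyme elevation > 5x baseline (grade 3 or greater"), the drug is withheld: "poly-ICLC will be held until that toxicity has reduced to Grade 1 or less". It then resumes at two-thirds of the original dose. If the toxicity recurs at that dose, the child continues the peptide vaccine without poly-ICLC.
- **Scale (6.2).** "Toxicity will be assessed according to the NCI Common Terminology Criteria for Adverse Events Version 5.0". Sections 9.6, 10.1.1 and 10.3.2 name the same scale. The CTCAE limits for ALT and AST are not reproduced, and no ULN is given.
- **Entry limit (3.2.1).** Adequate liver function includes "SGPT (ALT) ≤ 110 U/L", an absolute value. No AST limit is set.
- **RLT (6.3, repeated in 10.3).** "Any grade 3 or greater hematologic or non-hematologic toxicity with the exception of lymphopenia". Section 6.3 adds a time window and attribution to the vaccine. The RLT count feeds the first-3/first-6 rule in 10.1.4 and the accrual boundary in 10.3. Under section 6, freedom from RLT is also part of the condition for continuing after dose 8.
- **Frequency (5.1.5).** Events seen in at least 25% of patients include "alanine aminotransferase increased, aspartate aminotransferase increased, lymphocyte decreased". The same section reports one RLT among the 29 children treated in strata A and B.

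**The concern.** The trigger is written once as a multiple of the child's own baseline and once as a grade, as though the two always coincide. They need not, and the text gives no order of precedence. Two investigators with the same ALT value could then make different decisions on withholding and reducing poly-ICLC, each following part of the sentence. Enzyme rises are among the commonest events of the regimen, so the rule is likely to be consulted.

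There is a second possible route. A site that takes the parenthesis as a grading instruction could record grade 3 for a value that the named scale might grade lower. If the event were attributed to the vaccine, that label could enter the RLT count and the child's eligibility to continue after dose 8. Safety is the primary endpoint of Stratum C, the stratum enrolled after A and B completed accrual.

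**Working it through.** The plan attaches no computed figure to this trigger, so there is none to reproduce. The check is arithmetic on the plan's limits, followed by a comparison of readings.

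**Inputs.** Multiple of 5 (6.2.1); ALT entry limit of 110 U/L (3.2.1). Baseline ALT values are not in the documents, so those below are illustrative.

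**Step 1: where the multiple meets the entry limit.** 5 x baseline < 110 U/L exactly when baseline < 110 / 5 = 22 U/L.

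| Baseline ALT (U/L) | 5 x baseline (U/L) | Below 110? |
|---|---|---|
| 10 | 50 | yes |
| 15 | 75 | yes |
| 20 | 100 | yes |
| 22 | 110 | no (equal) |
| 30 | 150 | no |
| 40 | 200 | no |
| 110 | 550 | no |

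Over baselines of 10 to 110 U/L, the value that the parenthesis labels grade 3 runs from 50 to 550 U/L, an 11-fold spread.

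**Step 2: where the multiple could part from the grade.** This step rests on an assumption from outside the documents: for a normal baseline, grade 3 starts above 5 x ULN, with ULN between 30 and 55 U/L.

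- Grade 3 would start at 5 x 30 = 150 to 5 x 55 = 275 U/L.
- The two halves disagree for values above 5 x baseline and up to 5 x ULN, a band of width 5 x (ULN - baseline). For a baseline of 20 U/L the width is 5 x (30 - 20) = 50 to 5 x (55 - 20) = 175 U/L.
- The ratio of the thresholds is ULN / baseline. For baselines of 15 to 20 U/L it runs from 30 / 20 = 1.5 to 55 / 15 = 3.7.

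Example: baseline 20 U/L, on-treatment ALT 105 U/L. The multiple is met (105 > 100). The value is under the entry limit (105 < 110) and, on the assumption, under the start of grade 3 (105 < 150). One half of the trigger orders a hold and the other does not.

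**Step 3: can the sentence be read consistently?**

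- *The multiple governs.* Entry to the hold is on the baseline scale, but release is by grade, and no baseline multiple for grade 1 is stated. Entry and exit use different scales.
- *The CTCAE grade governs.* Entry and exit agree with each other and with 6.2, but the written multiple then has no function.
- *The parenthesis defines grade 3 for enzymes.* The hold and the RLT criterion then agree. However, the scale named in 6.2 is replaced for one laboratory test without saying so, and the release grade is still undefined on the baseline scale.

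No reading makes every part of the text operative.

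**The case against.** The strongest reply is that this is loose wording with limited reach, and several parts of that reply stand.

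- **The entry limit is not a grade.** A reader might infer that labelling a value below 110 U/L as grade 3 contradicts 3.2.1. It does not. Eligibility is decided once, whereas 6.2.1 concerns change from the child's own level on treatment. The comparison shows how low the multiple can reach, and no more.
- **RLT is already defined by grade.** A reader might infer that one ALT value must produce conflicting RLT decisions. The documents do not establish that. Sections 6.3 and 10.3 do not refer to the multiple, CTCAE v5.0 is named repeatedly, and 6.3 also requires attribution and timing. A wrong RLT would need a site to let a parenthesis in a dosing rule override the declared scale.
- **There is central review.** Under 9.8 and Appendix D, the PNOC Operations Office reviews all recorded adverse events weekly and discusses grade and attribution for those in question. This should catch some inconsistent grading. It does not tell a site which half of 6.2.1 to act on when a dose is due.
- **No effect on accrual rules can be quantified.** A reader might infer that mislabelling would noticeably raise the chance of suspension under 10.1.4 or 10.3. That needs an assumed shift in the RLT rate, which the documents do not supply. Their only related figure is 1 / 29 = 3.4% in strata A and B, without nivolumab.
- **The grading cut-offs are outside the documents.** Step 2 is therefore conditional, and varying the ULN does not remove the assumption about the grading rule.

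What remains is internal to the text: one trigger on two scales, no precedence, and a release condition on only one of them.

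**Conclusion.** The point holds as an inconsistency in the hold rule. From the documents alone, 6.2.1 equates a baseline multiple with a grade, 6.2 names a different scale, and the release grade has no counterpart on the baseline scale. It also follows from the documents alone that a baseline ALT below 22 U/L lets the multiple be met below 110 U/L.

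On the stated assumption (grade 3 above 5 x ULN for a normal baseline, ULN 30 to 55 U/L), the two thresholds differ by a factor of 1.5 to 3.7 for baselines of 15 to 20 U/L, so the same value can give different hold decisions. Spill-over into the RLT count, or into continuation after dose 8, is possible but of unknown size, and the documents show no instance of it. It is worth correcting because the event is common and the rule decides which children have poly-ICLC withheld and reduced.

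**What to change.** The sponsor should reconcile 6.2, 6.2.1, 6.3 and 10.3 so that one stated definition, on one scale, drives three things: the start of the hepatic hold, its release, and the grade used for RLT. The sponsor must choose that definition; this review takes no position on which threshold is right. Whatever is chosen, the multiple and the grade should not be presented as equivalent unless the text says when they are.

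The local ULN should be recorded with each ALT and AST value, so that the grade can be checked centrally against the recorded value and baseline.

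The cost is a wording amendment to 6.2.1, with a matching sentence in 6.3 and 10.3 if needed. Sites already submit their laboratory normals under Appendix B, so recording the ULN should add little work.
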